6.6.1 Primary Efficacy Endpoint

Primary efficacy endpoints include CR rate (CR+CRp+CRi+CRh) and DOR.

The CR rate will be assessed as the percentage of patients who achieve a CR, CRp, CRi, or CRh (as defined by the IWG 2003 and ELN 2010 criteria) after up to six cycles of combination therapy. The CR rate will be estimated, and the 95% confidence interval will be calculated.

DOR will be analyzed for the subset of patients who achieve an objective response as defined in Section 2.3.1. DOR is defined as the time from the initial response to the time of disease progression or death (whichever occurs first). If a patient is alive and has not experienced progressive disease before the end of the study, DOR will be censored at the day of the last cancer assessment. If no cancer assessments are performed after the date of the first occurrence of an objective response, DOR will be censored at the date of the first occurrence of an objective response plus 1 day.

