2.3 EFFICACY OBJECTIVES

2.3.1 Primary Efficacy Objective

The primary efficacy objective for this study is to evaluate the efficacy of atezolizumab administered in combination with Hu5F9-G4 to patients with R/R AML on the basis of the following endpoints:

- CR, CR with incomplete platelet recovery (CRp), CR with incomplete hematologic recovery (CRI), and CR with partial hematologic recovery (CRh) rate after up to 6 cycles of combination therapy, as determined by the investigator, according to the International Working Group (IWG) 2003 and European LeukemiaNet (ELN) 2010 criteria (Döhner et al. 2017)
- Duration of response (DOR), defined as the time from the initial response (CR, CRp, CRI, CRh, or partial remission [PR]) to the time of disease progression or death, whichever occurs first

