4.5.6 AML and Response Evaluations

Any evaluable or measurable disease must be documented at screening and re-assessed at each subsequent cancer evaluation. Patients should have AML evaluation and classification based on the 2010 ELN and 2017 ELN criteria (see [Appendix 5](#)). Disease prognosis should also be classified at screening using the modified ELN risk classification (see [Appendix 5](#)). Responses will be assessed by the investigator through use of the ELN recommendations (see [Appendix 5](#)).

Bone marrow examinations must include aspirate and biopsy (whenever possible) for morphology, flow cytometry, and routine cytogenetic and are required at screening. If fluorescence in situ hybridization (FISH) is performed at screening, FISH must be

performed during subsequent assessments. Refer to Section 4.5.7.2 for timepoints and requirements regarding collection of required bone marrow samples (aspirates and trephine/core biopsies) for exploratory biomarker studies. Bone marrow aspirates and biopsies are to be performed on Day 22 of Cycle 1 and subsequently after 3 and 6 months of study treatment (i.e., Day 1 of Cycles 4 and 7; see [Appendix 1](#)). Beyond 6 months of study treatment, bone marrow aspirates are required within 7 days prior to study drug administration on Day 1 of every 3 months (i.e., Day 1 of Cycles 10, 13, 16, etc.) (for determination of response), at the time of relapse or progressive disease, and at the end of treatment. For patients in follow-up who discontinue study treatment prior to disease progression, bone marrow aspirates and biopsy should be collected every 4 months (see [Appendix 1](#)). All bone marrow examinations should be assessed locally (see Section 4.5.3). Local institutional policies should be followed at any other time during the study when a bone marrow examination is deemed necessary by the investigator.

In addition, information on transfusion requirements prior to and during study treatment will also be collected (see [Appendix 1](#)).

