MLFS	Bone marrow blasts <5%, absence of blasts with Auer rods, absence of extramedullary disease, and no hematologic recovery required	Marrow should not merely be “aplastic;” at least 200 cells should be enumerated or cellularity should be at least 10%.
Partial remission	All hematologic criteria for CR, decrease of bone marrow blast percentage to 5% to 25%, and decrease of pretreatment bone marrow blast percentage by at least 50%	
Treatment failure		
Primary refractory disease	No CR or CR _i after six courses of investigational treatment, excluding patients who die as a result of aplasia or death because of indeterminate cause	

CR=complete remission; CR_i=complete remission with incomplete hematologic recovery; CR_{MRD-}=complete remission without minimal residual disease; MFC=multiparameter flow cytometry; MLFS=morphologic leukemia-free state; MRD=minimal residual disease; PD=progressive disease; RT-qPCR=real-time quantitative polymerase chain reaction.

^a Certain targeted therapies, for example, those inhibiting mutant IDH proteins, may cause a differentiation syndrome, that is, a transient increase in the percentage of bone marrow blasts and an absolute increase in blood blasts; in the setting of therapy with such compounds, an increase in blasts may not necessarily indicate progressive disease.

Appendix 5

Response Evaluation Criteria (cont.)

Category	Definition	Comment
Treatment failure (cont.)		
Death in aplasia	Deaths occurring \geq 7 days following completion of initial treatment while cytopenic, with aplastic or hypoplastic bone marrow obtained within 7 days of death, without evidence of persistent leukemia	
Death from indeterminate cause	Deaths occurring before completion of therapy or < 7 days following its completion, or deaths occurring ≥ 7 days following completion of initial therapy with no blasts in the blood, but no bone marrow examination available	
Response criteria for clinical trials only		

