Stable disease	
Absence of CR_{MRD-}, CR, CR_i, PR, MLFS, and criteria for PD not met
 
Evidence of an increase in percentage of bone marrow blasts and/or increase of absolute blast counts in the blood:
 
 • >50% increase in marrow blasts over baseline (a minimum 15%-point increase is required in cases with <30% blasts at baseline, or persistent marrow blast percentage of >70% over at least 3 months, without at least a 100% improvement in ANC to an absolute level ($>0.5 \times 10^9/L$ [500/μL], and/or platelet count to $>50 \times 10^9/L$ [50 000/μL] non-transfused), or • >50% increase in peripheral blasts (WBC \times % blasts) to $>25 \times 10^9/L$ ($>25 000/\mu L$) (in the absence of differentiation syndrome)^a or 	Period of stable disease that should last for at least 3 months

CR=complete remission; CR_i=complete remission with incomplete hematologic recovery; CR_{MRD-}=complete remission without minimal residual disease; MFC=multiparameter flow cytometry; MLFS=morphologic leukemia-free state; MRD=minimal residual disease; PD=progressive disease; RT-qPCR=real-time quantitative polymerase chain reaction.

^a Certain targeted therapies, for example, those inhibiting mutant IDH proteins, may cause a differentiation syndrome, that is, a transient increase in the percentage of bone marrow blasts and an absolute increase in blood blasts; in the setting of therapy with such compounds, an increase in blasts may not necessarily indicate progressive disease.

Appendix 5

Response Evaluation Criteria (cont.)

Category	Definition	Comment
Response criteria for clinical trials only (cont.)		
Progressive disease ^a	New extramedullary disease	
Relapse		
Hematologic relapse (after CR _{MRD} –, CR, CRi)	Bone marrow blasts $\geq 5\%$, reappearance of blasts in the blood, or development of extramedullary disease	
Molecular relapse (after CR _{MRD} –)	If studied pretreatment, recurrence of MRD, as assessed using RT-qPCR or by MFC	

ANC=absolute neutrophil count; CR=complete remission; CRi=complete remission with incomplete hematologic recovery; CR_{MRD}=complete remission without minimal residual disease; MFC=multiparameter flow cytometry; MLFS=morphologic leukemia-free state; MRD=minimal residual disease; PD=progressive disease; RT-qPCR=real-time quantitative polymerase chain reaction.

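### DOR counts partial remissions, but loss of a PR is not an event: return to a pretreatment marrow of 10–70% blasts leaves the patient counted as still responding

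*Combined protocol and SAP*

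**What the plan says.** Section 2.3.1 makes DOR a primary efficacy endpoint, "defined as the time from the initial response (CR, CRp, CRI, CRh, or partial remission [PR]) to the time of disease progression or death". Section 6.6.1 repeats this: "DOR is defined as the time from the initial response to the time of disease progression or death (whichever occurs first". On patients without an event it says "If a patient is alive and has not experienced progressive disease before the end of the study, DOR will be censored", at the last cancer assessment.

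Section 4.5.6 gives the criteria: "Responses will be assessed by the investigator through use of the ELN recommendations", which are set out in Appendix 5. Four parts of Appendix 5 matter here.

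- **Partial remission:** the hematologic criteria for CR, plus "decrease of bone marrow blast percentage to 5% to 25%, and decrease of pretreatment bone marrow blast percentage by at least 50" percent.
- **Progressive disease (PD), four routes:**
  1. A marrow rise of more than 50%, worded as "increase in marrow blasts over baseline (a minimum 15%-point increase is required in cases with" fewer than 30% blasts at baseline.
  2. Marrow blasts persistently above 70% for at least 3 months, without a stated improvement in neutrophils or platelets.
  3. A rise of more than 50% in peripheral blasts, to above 25 × 10⁹/L.
  4. New extramedullary disease.
- **Relapse:** hematologic relapse is defined after CR without MRD, CR or CRi, and molecular relapse after CR without MRD. PR, CRp and CRh are not listed.
- **Stable disease:** no response category met and PD not met.

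**The concern.** A duration-of-response endpoint should stop when the response stops. Here PR starts the clock, but nothing in the criteria is measured against the response value or the lowest marrow on study. A patient who leaves the PR range without reaching PD falls into stable disease, which is not a DOR event. Such a patient runs on to a later PD date or to death, or is censored at the last assessment as if still responding.

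There is a related gap for the better responders. Section 6.6.1 ends DOR at progression or death without mentioning relapse, whereas Section 2.3.2 names relapse from CR, CRp, CRh or CRi for both event-free and leukemia-free survival. Since Appendix 5 does not define relapse after CRp or CRh, those endpoints rely on an event that is not fully defined.

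At stake is the meaning of the DOR estimate: part of the reported duration may be time with the leukemia back at its pretreatment level.

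**Working it through.** The plan states no figure on this point, so the check applies the Appendix 5 rules to possible marrow values.

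**Inputs.** Let b be the pretreatment marrow blast percentage. The PD row says only baseline. Appendix 1 has one baseline marrow, taken at screening, and its footnote calls it pretreatment, so b is used for both.

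**PR range.** Blasts must be 5–25% and at most 0.5 × b. The lowest b that permits a PR is 5 / 0.5 = 10%. The highest permitted PR value is the smaller of 25 and 0.5 × b.

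**Route 1, marrow increase.** Blasts must exceed 1.5 × b. If b is below 30%, they must also reach at least b + 15, which is then the stricter condition.

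| Pretreatment b | PR values allowed | Route 1 level | Does return to b meet route 1? |
|---|---|---|---|
| 10% | 5% | 25% | No |
| 20% | 5–10% | 35% | No |
| 30% | 5–15% | 45% | No |
| 40% | 5–20% | 60% | No |
| 50% | 5–25% | 75% | No |
| 60% | 5–25% | 90% | No |
| 70% | 5–25% | 105%, impossible | No |
| 80% | 5–25% | 120%, impossible | No |

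The required level lies above b at every value, so a return to b never meets this route (0 of the 91 whole-number baselines from 10 to 100%). Blasts must rise at least three-fold from the highest permitted PR value; at b = 40% that is 60 / 20 = 3. Once b exceeds 100 / 1.5 = 66.7%, the route cannot be met at all.

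**Route 2, persistently above 70%.** On a return to b it can apply only if b is above 70%, and then only after at least 3 months.

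**Route 3, blood.** Section 4.1.1 requires WBC of at most 20 × 10³/µL before the first dose. Peripheral blasts at that point are therefore at most 20 × 10⁹/L, and a return to that level cannot exceed 25 × 10⁹/L.

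**Route 4, extramedullary.** It needs new disease outside the marrow; a marrow return does not supply it.

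**Relapse rows.** These do not apply after PR. Extending them unchanged would not work either: a PR marrow of 5–25% already meets the relapse line of 5% or more.

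**Example.** Take b = 40%, PR at 15%, then marrows of 30%, 40% and 55%. At 30% the PR is lost (above 25%, and above half of 40). At 40% the marrow is back at its pretreatment value, and at 55% it is above it. Route 1 needs more than 60%, so on marrow alone DOR is still running.

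**CR-type responders.** Take b = 40%, CR at 3%, then 20%. This is hematologic relapse in Appendix 5, but not PD (more than 60% needed), and relapse is not among the events in Section 6.6.1.

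**The case against.** A reader might infer that PR patients have no way to end DOR. That is too strong. Death, new extramedullary disease, the blood route and marrow blasts above 70% for at least 3 months all end it, and only the first PD route is tied to the baseline marrow. Where pretreatment blasts exceeded 70%, a full return can become an event, though late.

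A reader might also want the overstatement in days. The documents do not support one. It would need a regrowth rate and the time at which regrowth starts relative to marrow visits, which after 6 months are three cycles (84 days) apart. With fast regrowth, the first marrow after the PR may already show PD and nothing is overstated. With slow regrowth or a plateau, DOR can run to death or censoring.

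Three further objections have some weight:

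- **Other criteria.** Sections 2.3.1 and 6.6.1 cite IWG 2003 and ELN 2010, whose text is not reproduced. Section 5.3.5.10 allows progression on symptoms, but in rare cases and under adverse event recording. Appendix 5 is the set that Section 4.5.6 applies.
- **A loose reading of progression.** An investigator might treat any regrowth as progression. The censoring sentence in Section 6.6.1, however, refers to progressive disease, which is an Appendix 5 category.
- **Limited consequence.** There are 21 patients, no power basis, and no decision rule that uses DOR. Section 3.3.2 puts single-agent response at 10% or less. If 10% applied here (an assumption), about 21 × 0.10 = 2.1 responders would be expected. This limits the practical effect but does not make the rule correct.

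**Conclusion.** The point holds in this form: for pretreatment blasts of 10–70%, a PR patient whose marrow and blood return to the pretreatment level, with no new extramedullary disease, has no DOR event. Above 70% the event comes at least 3 months late. The error has one direction, because a missing or late event can only lengthen DOR. Its size cannot be stated from the documents, and the scan of baselines describes possible values, not the share of patients affected.

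The conclusion assumes that baseline in the PD row means the screening marrow, that Appendix 5 is the operative text, and that the pretreatment blood count is the one meeting the WBC limit before the first dose. The omission of relapse from Section 6.6.1, and of CRp and CRh from the relapse rows, rests on the text alone. This should be corrected before analysis because DOR is a primary efficacy endpoint.

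**What to change.** 1. Make the main DOR analysis, or at least a separately reported one, DOR among CR, CRp, CRi and CRh responders. End it at the first of Appendix 5 hematologic relapse (extended to cover CRp and CRh), PD or death.
2. If PR responders stay in DOR, pre-specify that documented loss of PR is also an event. Judge it against the response value or lowest on-study marrow value, or by return to the pretreatment blast level. Because PR also requires the CR hematologic criteria, say whether falling counts alone end it. Show DOR with and without PR patients.
3. State in Appendix 5 which sample is the baseline for the PD row.

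The cost is wording in the Synopsis, Sections 2.3.1 and 6.6.1 and Appendix 5, plus a derived date from marrows already scheduled. Treatment and visits do not change. Reported DOR may be shorter, the CR-type analysis has fewer patients, and the PR-inclusive version departs slightly from the ELN definition of PD, which should be noted in any comparison with outside data.

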2.3.2 Secondary Efficacy Objective

The secondary efficacy objective for this study is to make a preliminary assessment of the anti-neoplastic activity of atezolizumab administered in combination with Hu5F9-G4 to patients with R/R AML on the basis of the following endpoints:

- Objective response rate (ORR) achieved in the study, defined as the percentage of patients with a PR or better (i.e., CR+CRp+CRI+CRh+PR)
- Event-free survival (EFS), defined as the time from study entry to the date of induction treatment failure or relapse from CR, CRp, CRh, CRI, or death from any cause
- Leukemia-free survival (LFS), defined (only for patients achieving a CR, CRp, CRh, or CRI) as the time from the date of achievement of remission (CR, CRp, or CRI) until the date of relapse from CR, CRp, CRh, CRI, or death from any cause
- OS, defined as time from study entry to the date of death from any cause
- Progression-free survival (PFS), defined as the time from the first day of study treatment to disease progression or death, whichever occurs first
- Rate of transfusion independence, defined as the percentage of patients who achieve transfusion independence (i.e., achieving any continuous 56-day window without requiring platelet or RBC transfusions) at any time during study treatment

- Duration of transfusion independence, defined as the number of consecutive days of transfusion independence, measured from 1 day after the last transfusion to disease progression or subsequent transfusion

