Survival follow-up and anti-cancer treatment					x ^y

ADA=anti-drug antibody; ECHO=echocardiogram; ECOG=Eastern Cooperative Oncology Group; eCRF=electronic Case Report Form; ELN=European LeukemiaNet; HBcAb=hepatitis B core antibody; HBsAg=hepatitis B surface antigen; HBV=hepatitis B virus; HCV=hepatitis C virus; MUGA=multiple-gated acquisition (scan); PK=pharmacokinetic; Q2W=every 2 weeks; QW=once a week; QTcF=QT interval corrected through use of Fridericia's formula; RBR=Research Biosample Repository; T3=triiodothyronine; T4=thyroxine; TSH=thyroid-stimulating hormone.

Notes: On treatment days, all assessments should be performed prior to dosing, unless otherwise specified.

- ^a Patients who discontinue study treatment will return to the clinic for a treatment discontinuation visit not more than 30 days after their final dose of study treatment. The visit at which response assessment shows progressive disease may be used as the treatment discontinuation visit.
- ^b Informed consent must be documented before any study-specific screening procedure is performed and may be obtained more than 28 days before initiation of study treatment.
- ^c A pretreatment bone marrow aspirate and biopsy are required.
- ^d Vital signs will include measurement of respiratory rate, pulse rate, and systolic and diastolic blood pressures while the patient is in a seated position, and temperature. Vital signs (including resting, blood oxygen saturation measured by pulse oximetry) will be recorded during screening. Vital signs (not including pulse oximetry) will be measured prior to every injection of Hu5F9-G4. After Hu5F9-G4 administration, vital sign monitoring is not required unless clinically indicated. The patient's vital signs should be assessed up to 60 minutes prior to each atezolizumab infusion (see [Table 2](#)). Vital signs should also be recorded during or after the atezolizumab infusion if clinically indicated. Blood oxygen saturation, as measured by pulse oximetry (while the patient is at rest), should also be determined within 60 minutes before the first dose of atezolizumab.

Appendix 1

Schedule of Activities (cont.)

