Bone marrow aspirate and biopsy	x		x		x	x	x	x	x
Plasma sample		x	x	x	x	x	x	x	
Whole-blood sample		x	x	x	x	x	x	x	

Discon = discontinuation; NA = not applicable; PD = progressive disease; Tx = treatment.

^a Patients will undergo bone marrow biopsy sample collection, whenever possible, at the time of first evidence of disease progression. Biopsies should be performed within 14 days after progression or prior to the next anti-cancer therapy, whichever is sooner.

^b If bone marrow aspirate and/or biopsy are collected to confirm suspected PD, the bone marrow samples and the appropriate blood samples should be submitted for biomarker testing.

^c If the visit at which a response assessment shows relapse or PD resulting in patient discontinuation is used as the treatment discontinuation visit, then an additional sample for study treatment discontinuation does not need to be obtained.

^d For patients in follow-up who discontinue study treatment prior to disease progression, bone marrow aspirates and biopsy should be collected every 4 months. All bone marrow examinations should be assessed locally (see Section 4.5.7).

Appendix 4
Eastern Cooperative Oncology Group Performance Status Scale

Grade	Description
0	Fully active; able to carry on all predisease performance without restriction.
1	Restricted in physically strenuous activity but ambulatory and able to carry out work of a light or sedentary nature (e.g., light housework or office work).
2	Ambulatory and capable of all self-care but unable to carry out any work activities. Up and about >50% of waking hours.
3	Capable of only limited self-care; confined to a bed or chair >50% of waking hours.
4	Completely disabled. Cannot carry on any self-care. Totally confined to bed or chair.
5	Dead.

Appendix 5

Response Evaluation Criteria

Category	Definition	Comment
Response		
CR _{MRD-}	If studied pretreatment, CR with negativity for a genetic marker by RT-qPCR or CR with negativity by MFC	
CR	Bone marrow blasts <5%, absence of circulating blasts and blasts with Auer rods, absence of extramedullary disease, ANC $\geq 1.0 \times 10^9/L$ (1000/ μ L), and platelet count $\geq 100 \times 10^9/L$ (100,000/ μ L)	MRD ^a or unknown
CR _i	All CR criteria except for residual neutropenia ($< 1.0 \times 10^9/L$ [1000/ μ L]) or thrombocytopenia ($< 100 \times 10^9/L$ [100,000/ μ L])	

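### DOR and PFS name progression or death but not relapse, so a remitter who relapses below the Appendix 5 progression threshold has no clearly defined event

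*Combined protocol and SAP*

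**What the plan says.** **Endpoints.** Section 2.3.1 runs DOR from the first response (CR, CRp, CRi, CRh or PR) "to the time of disease progression or death, whichever occurs first". Section 6.6.1 repeats this, lists DOR as primary alongside the CR rate, and gives the censoring rule: "If a patient is alive and has not experienced progressive disease before the end of the study, DOR will be censored" at the last cancer assessment. Section 2.3.2 defines PFS as "the time from the first day of study treatment to disease progression or death, whichever occurs first". In the same list, EFS and LFS both name relapse as an event. Section 6.6.2 lists PFS among the endpoints to be analyzed but gives it no bullet.

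**Response criteria.** In Appendix 5, progressive disease by marrow requires ">50% increase in marrow blasts over baseline (a minimum 15%-point increase is required in cases with <30% blasts at baseline", with further routes through persistently high marrow blasts, peripheral blasts and new extramedullary disease. Hematologic relapse is a separate category: marrow blasts of at least 5%, "reappearance of blasts in the blood, or development of extramedullary disease". Molecular relapse has its own row.

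**Usage elsewhere.** Section 4.5.6 asks for marrow examination "at the time of relapse or progressive disease, and at the end of treatment". Appendix 3, footnote c, also keeps the terms apart: "If the visit at which a response assessment shows relapse or PD resulting in patient discontinuation is used as the treatment discontinuation visit". Appendix 1, footnote a, gives a closely similar visit rule with one term only: "The visit at which response assessment shows progressive disease may be used as the treatment discontinuation visit".

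**The concern.** In leukemia, remission normally ends with relapse, so relapse is the event one expects to close a DOR interval for a patient in remission. The DOR and PFS definitions do not name it, although EFS and LFS do, and Appendix 5 gives relapse and progressive disease different thresholds. A marrow or blood relapse can therefore fall short of progressive disease.

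Two analysts working from this text could date the same patient's event differently on a primary efficacy endpoint. One would stop the clock at relapse. The other would let it run to later progressive disease or death, or censor at the last assessment. On the second reading a patient's DOR could exceed the same patient's LFS. The consequence is for the reported duration and for its comparability with other studies.

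**Working it through.** The plan gives no event count, power or target for DOR or PFS, so there is no figure to reproduce. The check has four parts.

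**1. Does any section settle the question?**

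| Place | Treatment of relapse and progression |
|---|---|
| 2.3.1 and 6.6.1 (DOR), 2.3.2 (PFS) | Progression or death; relapse not named |
| 2.3.2 (EFS, LFS) | Relapse named |
| 4.5.6 (marrow schedule), 4.5.7.2, Appendix 3 footnote c | Relapse and progression named separately |
| 3.3.7, 4.5.3, Appendix 1 footnote a | Progression used alone, apparently in a broad sense |
| Appendix 3 footnote a | Disease progression used for a column that also covers relapse |
| 6.6.2 | PFS listed, no rule given |

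None of these says that relapse is, or is not, a DOR or PFS event.

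**2. How wide is the gap in marrow blasts?** Inputs are the two Appendix 5 definitions. Let *b* be the baseline blast percentage. I assume first that baseline means pretreatment.

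- Relapse: at least 5%, whatever *b* is.
- Progressive disease by percent increase, *b* below 30: the 15-point minimum binds because 0.5*b* is below 15, so the threshold is *b* + 15.
- Progressive disease by percent increase, *b* of 30 or more: above 1.5*b*.

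| Baseline | Threshold for progression | Relapse but not progression |
|---|---|---|
| 10% | 10 + 15 = 25% | 5% to under 25% |
| 20% | 20 + 15 = 35% | 5% to under 35% |
| 30% | above 1.5 × 30 = 45% | 5% to 45% |
| 40% | above 1.5 × 40 = 60% | 5% to 60% |
| 60% | above 1.5 × 60 = 90% | 5% to 90% |

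Since 1.5*b* = 100 at *b* = 66.7, the percent-increase route cannot be met at higher baselines. Since 1.5*b* = 70 at *b* = 46.7, above that baseline the separate route (blasts persistently over 70% for at least 3 months without the stated count improvement) can apply first. If baseline instead means a remission marrow of 2%, the threshold is 2 + 15 = 17% and the gap is 5% to under 17%. The gap narrows but does not close.

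In blood, any reappearance of blasts is relapse, while progression needs a rise of more than 50% to above 25 × 10⁹/L. A patient inside the marrow ranges could still progress by the blood route. New extramedullary disease meets both definitions, so that route is unambiguous. Appendix 5 has no relapse category after PR, so PR-only responders are outside the point.

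**3. Which way could the median move?** An affected patient's own time is equal or longer on the literal reading. The Kaplan-Meier median need not follow. Two invented examples:

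- *Three responders.* A relapses at month 1 and has progressive disease at month 3; B is censored at month 2; C has an event at month 5. Counting relapse: S(1) = 2/3, S(5) = 0, median 5 months. Literal reading: S(3) = 1/2, S(5) = 0, median 3 months (first time S is at most 0.5).
- *Five responders* with times 2, 3, 4, 6 and 8 months, the first four ending in relapse. Counting relapse: S = 0.8, 0.6, 0.4, median 4 months. If the first three relapses are below the progression threshold and are censored: S(6) = 1/2, median 6 months.

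The literal reading shortens the median in one example and lengthens it in the other.

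**4. How many patients contribute?** If the response rate equalled the single-agent ceiling of 10% in Section 3.3.2 (an assumption), 0.10 × 21 = 2.1, about 2 patients. At an assumed 30%, 0.30 × 21 = 6.3, about 6. Remitters who relapse below the progression threshold are a subset.

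**The case against.** The best defense is that the protocol often uses progression in a sense that includes relapse. Section 3.3.7 (treatment beyond progression), Section 4.5.3 and the follow-up marrow rule in 4.5.6 would be odd if a relapsed remitter still counted as not yet progressed. The DOR and PFS event is worded as disease progression; only the DOR censoring sentence uses the Appendix 5 label. Section 5.3.5.10 ties progression to IWG 2003 and the 2017 ELN recommendations, so Appendix 5 is not the only reference. This carries weight: it makes the literal reading less natural. It does not settle the matter, because 5.3.5.10 governs adverse event recording and other sections separate the two terms.

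EFS and LFS do capture relapse. But they are secondary, and LFS is limited to CR-type responders.

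A reader might infer more than the documents support:

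- *That the plan excludes relapse and so inflates DOR.* The text is ambiguous, and the median can move either way.
- *That the wide blast ranges are fixed by the protocol.* They depend on reading baseline as pretreatment. Appendix 5 does not define the word, and its partial remission row uses a different one.
- *That a study decision is at risk.* The design is descriptive, and the interim comparison in 6.6 concerns response data, not DOR.
- *That EFS has no usable event for patients without remission.* Appendix 5 has a treatment failure category close to what 2.3.2 calls induction treatment failure; the two are simply not linked.

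**Conclusion.** The point holds as an unresolved event definition. With Appendix 5 applied as written, a patient in CR, CRp, CRi or CRh who relapses in marrow or blood below the progression threshold has no DOR or PFS event at relapse. A baseline of 40% with relapse at 20% is an example: 20% is above 5% but not above 60%, assuming baseline means pretreatment and no other progression route is met. With a 2% remission marrow as baseline, the gap is 5% to under 17%.

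The effect on the reported DOR or PFS cannot be derived, in size or direction, and the number of affected patients is likely small. No stated decision depends on it. It still merits correction because DOR is a primary efficacy endpoint and the correction is almost free.

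**What to change.** - In 2.3.1, 2.3.2 and 6.6, define the DOR and PFS event as the earliest of hematologic relapse after CR, CRp, CRi or CRh, progressive disease, or death.
- In 6.6.1, censor DOR only for patients alive with neither relapse nor progressive disease.
- State whether molecular relapse counts, with the same answer for DOR, PFS, EFS and LFS.
- Give PFS its own censoring bullet in 6.6.2.

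Minor separate clean-up: reconcile the EFS event for patients without remission, which is induction treatment failure or death in 2.3.2 but progression or death in 6.6.2, and tie the former term to the Appendix 5 treatment failure category if it is kept. Add CRh to the LFS start date; CRh patients are already in the LFS population, so this is an editorial slip.

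The cost is wording. Relapse dates are already needed for EFS and LFS. Reported DOR or PFS may be shorter than under the literal reading.
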